6.2.3 PT Treatment Visits (In-clinic)

- Apply TENS during exercise treatment (TENS sites and NO TENS sites after day 65 if have in-clinic visit)

6.2.4 30 Day Research Homework (Home +/- 5 days)

- REDCap™ sends participant reminder email to complete Day 30 Research Homework
- Log into REDCap™ (or alternative method) to complete the following assessments
 - Adverse Events
 - Pre-treatment resting NRS for pain and fatigue
 - Pre-treatment Sit and Stand with NRS for pain and fatigue
- Apply TENS (or not)
 - PSFS
 - FIQR
 - BPI
 - PROMIS Physical Function
 - PROMIS-Sleep + Sleep duration
 - PCS
 - PHQ-8
 - GAD-7
 - PGIC
- Post-treatment resting NRS for pain and fatigue
- Post-treatment Sit and Stand test NRS for pain and fatigue
- REDCap™ sends email to study staff that Day 30 Research Homework is complete.

6.2.5 60 Day Research Homework (Home - 5/+10 days)

- REDCap™ sends participant reminder email to complete Day 60 Research Homework
- Log into REDCap™ to complete assessments:
 - Adverse Events
 - Pre-treatment resting NRS for pain and fatigue
 - Pre-treatment Sit and Stand Test with NRS for pain and fatigue
- Apply TENS (or not)
 - PSFS
 - FIQR
 - MAF
 - BPI

- PROMIS Physical Function
- PROMIS-Sleep + Sleep duration
- PCS
- PHQ-8
- GAD-7
- PGIC
- RAPA
- TAPS1
- Post-treatment resting NRS for pain and fatigue
- Post-treatment Sit and Stand Test with NRS for pain and fatigue
- REDCap™ sends email to study staff that Day 60 Research Homework is complete.

6.2.5.1 No TENS Group 65 Day Telehealth Visit by Study Team (Home -5/+15 days)

- Participants in no TENS clinics will be sent a TENS unit and electrodes with written instructions and links to video instructions for use through end of study.
- Study Team provides Telehealth instruction for TENS use, TENS app, and baseline Research Homework with TENS
- Participant completes Baseline Research Homework:
 - Log into REDCap™
 - Pre-treatment resting NRS for pain and fatigue
 - Pre-treatment Sit and Stand with NRS for pain and fatigue
- TENS applied for 1st full treatment X 30 minutes
 - Post-treatment resting NRS for pain and fatigue
 - Post-treatment Sit and Stand with NRS for pain and fatigue
- REDCap™ email sent to study staff when TENS instruction visit complete

6.2.6 90 Day Research Homework (Home +/- 5 days)

- REDCap™ sends participant reminder email to complete Day 90 Research Homework
- Log into REDCap™ to complete assessments:
 - Adverse Events
 - Pre-treatment resting NRS for pain and fatigue
 - Pre-treatment Sit and Stand Test with NRS for pain and fatigue
- TENS applied X 30 minutes
 - PSFS
 - FIQR
 - BPI
 - PROMIS Physical Function
 - PROMIS-Sleep + Sleep duration
 - PCS
 - PHQ-8
 - GAD-7
 - PGIC
- Post-treatment resting NRS for pain and fatigue
- Post-treatment Sit and Stand with NRS for pain and fatigue
- REDCap™ email sent to study staff after Day 90 Research Homework is complete

6.2.7 180 Day Research Homework (Home +/- 5 days)

- REDCap sends participant reminder email to complete Day 180 Research Homework
- Log into REDCap™ to complete assessments:
 - Adverse Events
 - Pre-treatment resting NRS for pain and fatigue
 - Pre-treatment Sit and Stand Test with NRS for pain and fatigue
- TENS applied X 30 minutes (all participants)
 - PSFS
 - FIQR
 - MAF
 - BPI
 - PROMIS Physical Function
 - PROMIS-Sleep + Sleep duration
 - PCS
 - PHQ-8
 - GAD-7
 - RAPA
 - PGIC
 - TAPS1
 - Concomitant Medications
 - Barriers to TENS
- Post-treatment resting NRS for pain and fatigue
- Post-treatment Sit and Stand Test with NRS for pain and fatigue
- REDCap™ email sent to study staff when Day 180 Research Homework is complete

6.2.8 Study Intervention Discontinuation Evaluations/procedures

Participants will be allowed to keep and continue to use the TENS devices following completion of the study, but electrodes will no longer be supplied. Individual participants may discontinue treatment at their discretion but will be encouraged to continue use through the end of the trial and even if they stop using TENS to complete all assessments as scheduled. If a participant develops a contraindication to TENS use during the study (such as pregnancy), they will be discontinued from treatment but not from the study. Adverse events will be collected at all routine assessments. The only reason we will not attempt to obtain all the assessment information is withdrawal of consent.

6.2.9 Final On-Study Evaluations

Final on-study evaluations are at the Day 60, 90 or 180-day assessment as described above.

6.2.10 Protocol Deviations

Protocol deviations are not being collected in this study.

6.2.11 Documentation of Fibromyalgia

FM diagnosis by criteria will be performed using the 2016 ACR criteria. Participants may be enrolled even if they do not meet criteria if they have been told by a clinician that they have FM. Criteria-based diagnosis will be used as a variable for statistical analysis. Physical therapists will not be asked to make the FM diagnosis themselves.

6.2.12 Concomitant Medications/Treatments

We will collect categories of concomitant medications used for pain, anxiety/depression, and sleep on a dedicated case report form. We will also collect information on substance use with the TAPS1 instrument at enrollment and at the end of the study.

6.2.13 Clinical Assessments

Patient-reported outcomes will be obtained, but no other clinical parameters will be measured. TENS-specific adverse events and serious adverse events will be recorded on the CRFs.

6.2.14 Questionnaires

The following questionnaires will be self-administered by participants:

- **Resting NRS for pain and fatigue**-11-point scale
- **Sit and Stand Test** – quantifies movement-evoked pain and fatigue.
- **2016 FM Criteria**- diagnostic criteria for fibromyalgia.
- **PSFS (Patient Specific Functional Scale)** – quantifies activity limitation and measures functional outcomes
- **FIQR (Fibromyalgia Impact Questionnaire Revised)**- 21 items used to evaluate function, overall impact, and symptoms in patients with fibromyalgia.
- **MAF (Multidimensional Assessment of Fatigue)**-16 items measuring fatigue according to four dimensions: degree and severity, distress that it causes, timing of fatigue, and impact on various activities of daily living.
- **BPI (Brief Pain Inventory)**- 11 items measuring pain severity and interference with daily activities.
- **PROMIS-Physical function** – assesses information about physical activities.
- **PROMIS-Sleep+Sleep duration**- 8 items + sleep duration assesses sleep quality and quantity
- **PCS (Pain Catastrophizing Scale)**- 13 items measuring pain magnification, rumination, and helplessness.
- **PHQ-8 (Personal Health Questionnaire Depression Scale)**- 8 items measuring depressive disorders.
- **GAD-7 (Generalized Anxiety Disorder)**- 7 items measuring severity of various signs of generalized anxiety disorder.
- **RAPA (Rapid Assessment of Physical Activity)**- 9 items evaluating current level of physical activity.
- **TAPS (Tobacco, Alcohol, Prescription Medication, and other Substance use)**- 4 item screening tool for substance abuse.

- **PGIC (Patient Global Impression of Change)**- one item evaluating all aspects of patients' health and assesses if there has been an improvement or decline in clinical status.

6.2.15 Participant Adherence Assessments

We will routinely analyze TENS usage electronically as provided by the device. If participants are not using the TENS as prescribed, we will inform the physical therapist and follow up with text, email, or phone calls with the participant to encourage usage.

7 MANAGEMENT OF ADVERSE EXPERIENCES

7.1 Adverse Event Reporting

An adverse event in this study will be defined as an unfavorable and unintended sign or symptom temporally associated with the use of the TENS unit, falls while performing the Sit and stand Test during Research Homework, or another unfavorable sign or symptom limited to problems associated with specific study activities, fibromyalgia symptoms, or hospitalizations/ED visits (see Question 2 below). Pain associated with physical therapy treatment may worsen during the study but will not be classified as an AE.

Adverse events will be queried and recorded on the Participant Experience CRF at each data collection (days 30, 60, 90, and 180) by asking participants the following questions:

"STUDY RELATED

Have you experienced any of the following problems since your last report? (check all that apply)

- Fell during sit and stand test
- Fell or injured yourself during physical therapy exercise at home
- None of the above

Have you had any of the following changes to your health since your last report?

- A pacemaker, implanted neurostimulator or any other implanted device
- A new diagnosis of epilepsy
- A new diagnosis of cancer
- Have become pregnant
- None of the above

Did you experience any of the following since your last report?

Hospitalization? Yes No

i. If yes, please explain: _____

ii. Was the hospitalization related to your TENS use? Yes No

Emergency room visit? Yes No

i. If yes, please explain: _____

ii. Was the emergency room visit related to your TENS use?

TENS RELATED

Have you experienced any problems using the TENS units or electrodes since your last report? Yes No

If yes, what type of problem did you experience? (check all that apply)

- Anxiety with TENS
- Itchiness with TENS
- Nausea with TENS
- Pain with TENS
- Skin irritation with electrodes
- Other TENS related problems

Please list other problems: _____

Adverse events that are reported to study staff outside of regularly scheduled homework where the study team is recommending discontinuing TENS use or where the participant discontinued TENS use on their own will be collected by the study team and reported in REDCap on the Participant Experience Review Form. For any serious adverse events reported outside of regularly scheduled homework, the information will be collected by study staff and forwarded to the medical safety monitor who will review the information for a determination regarding the safety of the subject continuing TENS use in the study. The monitor will complete the Participant Experience Review Form, which will be entered into REDCap.

Anticipated adverse events with TENS use include:

- Skin rash or irritation from electrodes
- Pain with TENS

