2.3 Risk/Benefit Assessment

The following are potential risks associated with the TENS unit:

1. Local skin irritation, caused by the adhesive in the TENS electrode pad, may occur.
2. Mild redness at the site of the TENS stimulation and a burning or pricking sensation if insufficient gel is used.
3. Discomfort or aggravation of pain from TENS.

Potential benefits of TENS include:

1. Reduced pain and fatigue at rest or with movement.
2. Improvement in symptoms of FM.
3. Improvement of functional status.
4. Reduced medication use.

An additional risk associated with the Sit and Stand Test is the potential for falls when completing this test at home.

There is a potential risk to personal information by connecting to a fraudulent or incorrect Quell app when study participants download the incorrect app for use with the TENS units. To prevent the download of an incorrect app to be used with the TENS units, instructions are given to study participants to only download the app during training sessions with study staff.

There is a possibility that the TENS unit could malfunction and increase the level of intensity on its own. If a potentially defective unit is identified by a participant with this issue, participants are advised to discontinue use of the unit and to alert the study team. The study team will send a prepaid box for the return of the unit and will replace the potentially defective unit with a new unit.

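### The step lists put the adverse event form before each session's Sit and Stand tests and TENS, the schedule table puts it after; under the lists, each participant's last session has no scheduled adverse event question

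*Protocol*

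**What the plan says.** Protocol 7.1 sets the schedule: "Adverse events will be queried and recorded on the Participant Experience CRF at each data collection (days 30, 60, 90, and 180". The study-related part of the form opens with "Have you experienced any of the following problems since your last report? (check all that apply" and offers "Fell during sit and stand test" as a tick-box. The TENS part asks "Have you experienced any problems using the TENS units or electrodes since your last report". Both look backward only, and no date field is shown for a fall.

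Protocol 6.2.4 to 6.2.7 lay out the Day 30, 60, 90 and 180 sessions in one order: log in, adverse events, pre-treatment resting ratings, pre-treatment Sit and Stand Test, TENS (or not), questionnaires, post-treatment ratings, post-treatment Sit and Stand Test, completion email. The schedule table in 6.1 has its adverse event row below the post-treatment Sit and Stand row.

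Neither the table nor sections 6.2.2 and 6.2.5.1 show an adverse event form at Day 1 or Day 65. Section 6.2.8 nevertheless says "Adverse events will be collected at all routine assessments".

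Protocol 2.3 recognises the hazard: "An additional risk associated with the Sit and Stand Test is the potential for falls when completing this test at home". Section 7.1 makes such falls adverse events by definition. For events reported outside scheduled homework, 7.1 says those "where the study team is recommending discontinuing TENS use or where the participant discontinued TENS use on their own will be collected"; serious events go to the medical safety monitor. Sections 3.2 and 6.2.9 allow the final session to be Day 60, 90 or 180. SAP section 10 defines adverse events but gives neither the form's place in the session nor the period over which events are tabulated.

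**The concern.** A form that looks back to the previous report and is completed at the start of a session cannot record what happens later in that session. The event is first asked about at the next form, and after the last session there is no next form. Falls during the home test are a risk the trial itself introduces, so they should be ascertained fully.

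The same displacement matters at Day 60, where the controlled period ends. PT-only participants receive TENS after that session and do a Day 65 session with no form of its own. Their next form, at Day 90, therefore mixes events from the end of the controlled period with events under TENS. In the TENS arm, a problem during the 30-minute TENS session that precedes the primary outcome measurement is missing from the Day 60 form. Section 8 of the protocol reacts to unanticipated events above 5% of enrolled participants, and any such event missed at a last session would lower that count.

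**Working it through.** There is no stated figure on this point to reproduce. The check is a count of tests against forms.

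**Inputs.**
- Two Sit and Stand tests per homework session, before and after treatment (6.2.2 to 6.2.7).
- Sessions: Days 1, 30, 60, 90 and 180 in the TENS arm; the same plus Day 65 in the PT-only arm (6.1).
- Forms: Days 30, 60, 90 and 180 (7.1), placed first in the session (6.2.4 to 6.2.7).

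**Formula.** Tests with no later form = 2 × (sessions from the last form onward). The session containing the last form counts, because its tests follow the form. A Day 65 session after the Day 60 form counts too.

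| Last session attended | TENS arm | PT-only arm |
|---|---|---|
| Day 1 | 2 of 2 | 2 of 2 |
| Day 30 | 2 of 4 | 2 of 4 |
| Day 60 | 2 of 6 (33%) | 2 of 6 (33%) |
| Day 65 | not applicable | 4 of 8 (50%) |
| Day 90 | 2 of 8 (25%) | 2 of 10 (20%) |
| Day 180 | 2 of 10 (20%) | 2 of 12 (17%) |

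For homework TENS sessions, one is uncovered at the end of every TENS-arm path: 1 of 5 if Day 180 is last. For PT-only participants it is 1 of 3 at Day 180, and the only one they have done if they stop after Day 65.

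**Controlled period.** Each arm has 3 sessions × 2 = 6 tests on Days 1, 30 and 60. The Day 30 form covers the Day 1 tests and the Day 60 form covers the Day 30 tests, so 4 of 6 are covered through Day 60 in both arms. The plan expects 450 × (1 − 0.24) = 342 participants to complete Day 60, so 342 × 2 = 684 Day 60 tests would fall on the Day 90 form or on none.

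**What the Day 90 form covers.** TENS arm: the 2 Day 60 tests. PT-only arm: the 2 Day 60 tests plus the 2 Day 65 tests, 4 in all, together with the first weeks of TENS use.

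**Recall delay.** By the windows in 6.1, Day 60 falls on days 55 to 70 and Day 90 on days 85 to 95. An event in the Day 60 session is asked about between 85 − 70 = 15 and 95 − 55 = 40 days later. Day 180 falls on days 175 to 185, so an event in the Day 90 session waits between 175 − 95 = 80 and 185 − 85 = 100 days.

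**With the form last.** The uncovered count falls to 0 for anyone whose last session is Day 30, 60, 90 or 180. It stays at 2 of 8 for PT-only participants who stop after Day 65 and at 2 of 2 for those who do only Day 1, unless those sessions also get a form. With both added it is 0 on every path.

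**The case against.** **The order is not settled.** From the resting ratings onward the schedule table runs largely in session order and ends with adverse events after the post-treatment test. The step lists never say that their item order is binding, and the order of two questionnaires differs between Days 60 and 180. This stands in part. The table is not chronological throughout, since the functional scale precedes consent, and all four lists agree in putting the form first. The order used in REDCap cannot be read from the documents, so the conflict is itself part of the point.

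**Participants who leave are asked why.** A reader might infer that a fall or reaction that makes someone quit is never asked about. The documents do not support that. Protocol 4.4 has staff contact those who withdraw and complete a termination form, and protocol 9.4 and SAP 7.3 have drop-out reasons recorded and compared between arms. The 7.1 route takes in serious events and those tied to stopping TENS. What remains is narrower: a reason for withdrawal is not the fall and TENS checklist, and completers are not withdrawn and so not contacted.

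**Most sessions are picked up later.** Events in the Day 1 and Day 30 sessions are asked about on the next form for anyone who continues. Only events during or after the Day 60 session, not all events up to Day 60, move to the Day 90 form. This stands.

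**The randomised comparison is not biased.** A reader might infer that the comparison between arms is damaged. Coverage through the Day 60 form is equal (4 of 6 tests per arm), and neither document plans a between-arm test of adverse events. The loss is of information, and it is balanced.

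**Tests are not events.** The fractions count opportunities. For TENS reactions, up to 2 hours daily over 180 days is up to 360 hours, of which one 30-minute session is 0.5/360 = 0.14%. This stands for TENS problems in general. It does not apply to falls in the test, which can occur only in these sessions.

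**Conclusion.** The point holds in a limited form. The protocol contradicts itself on where the adverse event form sits. Under the step lists, a non-serious fall or TENS problem in the last session has no scheduled question: 2 of 10 tests for TENS completers, 2 of 12 for PT-only completers, 2 of 6 when Day 60 is last, and 4 of 8 for PT-only participants who stop after Day 65. Withdrawal contact, drop-out reasons and the unscheduled route reduce this gap without closing it.

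Events in the Day 60 session first appear on the Day 90 form. For PT-only participants, a fall in that session cannot then be told apart from one at Day 65, because the fall item as reproduced in 7.1 has no date. A safety summary through the Day 60 form is balanced between arms but omits the Day 60 session.

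This rests on two assumptions: that the step lists, and not the table, describe the order used, and that participants answer the form literally. The documents give no fall rate, so the number of events lost cannot be estimated. The matter concerns safety ascertainment and leaves the primary efficacy analysis untouched. It is worth correcting because the correction is cheap.

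**What to change.** - Make the Participant Experience CRF the last item, after the post-treatment Sit and Stand Test, at Days 30, 60, 90 and 180. State this in 6.2.4 to 6.2.7 and align the 6.1 table with it.
- Add the same short form at the end of Day 65. Add it at the end of Day 1 too, where the gain is for participants who do not continue. This also brings practice into line with the statement in 6.2.8.
- In SAP section 10, state that the randomised safety summary uses forms up to and including Day 60, and that later forms are reported separately.
- Flag visits completed with the form first, and report by arm how many there were, since their coverage through Day 60 is 4 of 6 tests and not 6 of 6.

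The cost is a reordering in REDCap, two short forms and slight added burden. The real downside is that a form placed last may be skipped when a session is left unfinished. Staff should therefore check for it before treating a session as complete.

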Participants will be identified after they are referred for PT for treatment of FM or chronic pain (pain lasting more than three months). At their first (intake) physical therapy visit, they will be provided information about the study that can be accessed on paper or on-line. They will perform an electronic screening form on the first visit if interested in participating. Participants will provide eConsent after eligibility is confirmed at the initial PT visit. At the second PT visit after eConsent is signed, participants will be provided a link to access their survey queue within REDCap™ for data capture and accessing the case report forms. Participants enrolled at a TENS site will then be instructed in use of TENS and the TENS unit with electrodes will be provided. Those participants enrolled at a no TENS site will skip the instruction in use of TENS and TENS units will not be provided until after day 60 assessments are completed at which time they will be instructed in use of TENS by the study team remotely. All participants will be instructed to capture baseline assessments at home (called Research Homework) before their next PT visit. Pain and fatigue will be rated before and following their first TENS treatment (or no TENS) at home (day 1). At 30, 60, 90, and 180 days following enrollment, participants will complete all assessments at home, including pain ratings at rest and with movement along with questionnaires (see below for a list of questionnaires).

Interventions and Duration

For the TENS group, participants will be given TENS devices and electrodes following enrollment during their second PT visit. TENS will be applied to the upper and lower back with butterfly electrodes using the following parameters: mixed frequency (2-125Hz), strong but comfortable intensity, variable pulse duration from 100-250 microseconds. TENS will be applied at home when the patient is active and doing exercises for 2 hours per day and should be brought back to PT visits and used during PT treatment.

For the no TENS group, participants will be given TENS units after the primary endpoint is collected at 60 days. After completion of research homework for Day 60, TENS units will be mailed to the participants. The same instructions for use will be given to the participants as were given to the participants in the TENS group. TENS instructions will be done virtually with a study team member.

Sample Size and Population

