3.2 End of Study Definition

The primary endpoint of movement-evoked pain is assessed at Day 60. The end of the study will be the final Day 180 assessment or March 11, 2025, whichever comes first. All patient reported measures will be assessed at Day 180 for those who reach Day 180 prior to or on March 11, 2025, or at Day 60 or Day 90 for participants who will not reach Day 180 by March 11, 2025.

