5 STUDY INTERVENTIONS/STUDY MEDICATION/STUDY DEVICE

5.1 Study Intervention, Administration, and Duration

Participants in the TENS group will be given two TENS devices and electrodes on PT Visit 2. TENS will be applied to the upper and lower back with butterfly electrodes using the following parameters: mixed frequency (2-125Hz), strong but comfortable intensity, variable pulse duration from 100-250 microseconds. TENS will be applied during PT exercise treatment at the clinic and will be used at home when the patient is active or while doing exercise/activity for up to 2 hours per day.

The participants enrolled in the TENS group will use the device during the time of their PT (expected to be approximately 6 weeks but variable according to the individualized PT treatment plan), and after they complete PT for a total of 180 days.

Participants enrolled in the no TENS group will receive TENS units and electrodes after they

complete the primary outcome assessments at 60 days following enrollment to use for the next 120 days. All participants will be allowed to keep their TENS units after the study.

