6 CLINICAL EVALUATIONS/STUDY PROCEDURES

6.1 Schedule of Activities

Evaluation	First and Second PT Intake Visit*	Research Homework before PT Visit 3 (Day 1 ¹)	Treatment Visits	30 +/- 5 days Home ¹	60 - 5/+10 days Home ¹	65 - 5/+15 days Home (No TENS Group Only) ⁴	90 +/- 5 days Home ¹	180 +/- 5 days Home ¹
Eligibility Screen- REDCap™	X							
PSFS		X		X	X		X	X
Informed Consent/ eConsent Review	X*							
Resting NRS pain/fatigue ²		X		X	X	X	X	X
Sit and Stand Test with NRS pain and fatigue pre-treatment ³		X		X	X	X	X	X
TENS applied (or not) x 30 minutes		X	X	X	X	X	X ³	X ³
Demographics		X						
2016 FM Criteria		X						
FIQR		X		X	X		X	X
MAF		X			X			X
BPI		X		X	X		X	X
PROMIS-Physical Function		X		X	X		X	X
PROMIS-Sleep		X		X	X		X	X
PCS		X		X	X		X	X
PHQ-8		X		X	X		X	X
GAD-7		X		X	X		X	X
RAPA		X			X			X
PGIC				X	X		X	X
TAPS1		X			X			X

Concomitant Medications		X						X
Sit and Stand Test with NRS pain and fatigue post TENS or no TENS treatment after 30 min of answering questionnaires		X		X	X	X	X ³	X ³
Adverse Events				X	X		X	X
Barriers to TENS								X

* *Informational activities (e.g., video explaining study, description of TENS) will be delivered at home between PT visits. Consent will be obtained electronically before or as the initial activity of the second PT visit. After the second PT visit, participants will complete Research Homework. Day 1 is designated as the day the baseline study data is collected at home. Baseline data collection should be completed within 10 days of the second PT visit.*

¹*Assessment completed on computer or tablet, phone, or paper at home. If the participant does not have access to a computer, the data will be collected over the phone by the study team and directly entered into the database, or on paper/mailed or Faxed.*

²*Resting NSR pain/fatigue and Sit and Stand Test completed pre and post TENS treatment.*

³*All participants apply TENS*

⁴*Day 65 visit is only performed by the No Tens group*

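### No adverse-event form is scheduled at Day 65, the PT-only arm's first TENS session, and PT-only participants with no later assessment have no scheduled harm query after receiving TENS

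*Protocol*

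**What the plan says.** **When harms are asked about.** Protocol 6.2.8 is general: "Adverse events will be collected at all routine assessments". Section 7.1 is specific: "Adverse events will be queried and recorded on the Participant Experience CRF at each data collection (days 30, 60, 90, and 180". The Adverse Events row of the schedule table (6.1) is marked at Days 30, 60, 90 and 180 and is blank at Day 65. The visit lists for those four days each include an adverse-event item; the list for Day 65 (6.2.5.1) has none.

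**What happens at Day 65.** The table footnote says: "Day 65 visit is only performed by the No Tens group". The Day 65 list includes "TENS applied for 1st full treatment X 30 minutes", with resting ratings and a Sit and Stand Test before and after. Its title gives the window: "6.2.5.1 No TENS Group 65 Day Telehealth Visit by Study Team (Home -5/+15 days".

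**Who receives TENS.** The Synopsis says of the no-TENS group: "After completion of research homework for Day 60, TENS units will be mailed to the participants". Section 5.1 has them receive units after they "complete the primary outcome assessments at 60 days following enrollment to use for the next 120 days". Section 4.3.1 also provides units after Day 60. None of the three states an exception.

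**When follow-up can end.** Section 3.2 allows final patient-reported measures "at Day 60 or Day 90 for participants who will not reach Day 180 by March 11, 2025". Section 6.2.9 likewise lists Day 60 among the possible final evaluations.

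**The concern.** Day 65 is a scheduled data collection with its own column, window and REDCap entries, so it is natural to count it as a routine assessment under 6.2.8. It is also the PT-only arm's first exposure to the device, self-applied at home after remote instruction. Section 2.3 lists skin irritation, discomfort or worse pain from TENS, and falls during the Sit and Stand Test as the risks, and all of these can arise at that session.

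What is at stake is how completely TENS harms are captured after the control arm crosses over. Someone who receives a unit and has no later form contributes exposure but no solicited information. Protocol 8 and SAP 10.3 also set a trigger for changing the consent form and the queries when an unanticipated event occurs in more than 5% of enrolled participants. Events that nobody asks about can only lower that count.

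**Working it through.** There is no figure in the plan to reproduce. The check is a comparison of sections, followed by date arithmetic.

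**Step 1. Form schedule against first TENS use**

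| Arm | First TENS use | Form that day? | Next scheduled form |
|---|---|---|---|
| TENS | Day 1 homework | No | Day 30 |
| PT-only | Day 65 session | No | Day 90 |

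In the Day 60 list the adverse-event item comes first, and units are mailed only after that homework is done. The Day 60 form therefore always precedes PT-only exposure.

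**Step 2. Delay for those who reach Day 90**

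- Nominal: 90 − 65 = 25 days.
- Protocol windows: Day 65 (−5/+15) is Day 60 to 80; Day 90 (±5) is Day 85 to 95. Shortest 85 − 80 = 5 days; longest 95 − 60 = 35 days.
- SAP Table 5.1 gives Day 65 a ±5 window (Day 60 to 70), so the shortest is 85 − 70 = 15 days and the longest is still 35.
- TENS arm for comparison: 30 − 1 = 29 days nominal.

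The questions in 7.1 reach back to the previous report, so a Day 90 form covers the Day 65 session in retrospect.

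**Step 3. How many have the delay**

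Planned enrolment is 450, half of the clinics per arm, with 24% drop-out: 225 × 0.76 = 171 PT-only participants completing Day 60. This is an upper bound on those who reach Day 65.

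**Step 4. Participants with no later form**

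The study closes on 11 March 2025. Latest start dates to reach each point:

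- nominal Day 60: 10 January 2025
- nominal Day 65: 5 January 2025
- earliest Day 90 (Day 85): 16 December 2024
- nominal Day 90: 11 December 2024

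The broad group is those who reach Day 60 but not nominal Day 90: 90 − 60 = 30 days of starts. The narrow group is those who reach nominal Day 65 but not even the earliest Day 90: 85 − 65 = 20 days of starts.

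The documents give 30 months of recruitment but no closing date. Assume even accrual of 450 over 24, 30 or 36 months, still open at that time, with half in PT-only clinics.

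PT-only count = (450 / months) × (days / 30.44) × 0.5, then × 0.76 for drop-out.

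| Months | 20 days: all starters / after drop-out | 30 days: all starters / after drop-out |
|---|---|---|
| 36 | 4.1 / 3.1 | 6.2 / 4.7 |
| 30 | 4.9 / 3.7 | 7.4 / 5.6 |
| 24 | 6.2 / 4.7 | 9.2 / 7.0 |

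The range is about 3 to 9. If enrolment closed before mid-December 2024 it is 0. The documents give no rate for loss between Day 65 and Day 90, so that group cannot be sized.

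**Step 5. The remaining route**

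For events outside scheduled homework, 7.1 relies on the event being reported to staff. It provides for recording where TENS is stopped, on the team's recommendation or by the participant, and where the event is serious. It makes no clear provision for a rash or pain in someone who carries on using the device.

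**The case against.** The strongest reply is that the arms are treated alike. The TENS arm also starts TENS and performs two Sit and Stand tests on Day 1 with no form, and waits slightly longer (29 days against 25) for its first query. Together with the recall wording, this makes the Day 65 omission look like a consistent choice. That stands for everyone who reaches Day 90: their information is delayed, not lost. It does not help those with no later form. A TENS-arm participant followed only to Day 60 still has two scheduled forms after exposure; a PT-only participant in the same position has none.

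A reader might go further and infer that these PT-only participants are never asked about harm. The documents do not support that. They are asked at Days 30 and 60, before exposure. Staff also have contact with them at the Day 65 telehealth instruction and when following up low device use (6.2.15). None of this is a systematic harm query.

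It is also fair to say that the Day-60-final group is inferred. No section says whether these participants still have the Day 65 session, and 120 days of use cannot fit within the study for them. The supply statements are nevertheless unconditional, and the silence itself needs resolving.

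Two cautions about the remedy hold. A form at the end of a 30-minute session will miss later skin reactions, so it supplements the Day 90 form and does not replace it. It also gives PT-only participants an earlier first query after exposure than the TENS arm had, so first-use harms in the two arms should not be compared without noting this.

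**Conclusion.** The concern holds in a limited form. Section 6.2.8 conflicts with 6.1, 6.2.5.1 and 7.1 over Day 65, and 3.2 and 6.2.9 do not fit with the unconditional supply of units in the Synopsis, 4.3.1 and 5.1. The consequence is delayed recall for up to about 171 PT-only participants, and no scheduled query after receiving TENS for those lost between Day 65 and Day 90 or finishing at Day 60. The second of these groups is about 3 to 9 people under even accrual still open in December 2024 to January 2025, and 0 otherwise.

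A reader might also conclude that a planned TENS harm rate is biased low. The SAP safety section defines no TENS-exposed denominator, so no specified estimate can be said to be biased. What can be said is that safety information after crossover is incomplete. The primary comparison at Day 60 is unaffected, because PT-only participants receive TENS only after it.

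**What to change.** Reconcile 6.2.8 with 6.1, 6.2.5.1 and 7.1, and reconcile 3.2 and 6.2.9 with the Synopsis, 4.3.1 and 5.1, as follows:

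- Add the existing Participant Experience CRF to the Day 65 REDCap session, and mark it in the schedule table and in 7.1.
- Send the same form once at the end of study to PT-only participants who received TENS and have no later scheduled assessment.
- State what happens at Day 65 for participants whose final assessment is Day 60, and align the Day 65 window between the Protocol and SAP Table 5.1.
- When summarising TENS harms in PT-only participants, report how many exposed participants had no query after exposure. Do not drop them from the denominator: people who stop after a reaction may be less likely to respond, so a responder-only rate could itself be biased.

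The cost is one existing electronic form in an existing session, one automated survey for a few people, and a minute or two of participant time. The change concerns data collection only; it sets no dose or clinical rule.
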